9.4.2. Safety Analyses

All AEs occurring during the study will be recorded and classified according to MedDRA terminology. Those occurring during or after treatment are considered as treatment-emergent. All reported TEAEs will be summarized, in terms of the number of subjects reporting events, system organ class, preferred term, severity, relationship to study drug, and seriousness. For summarization of event causality and seriousness, subjects will be counted only once within a system organ class or preferred term using the event with the greatest relationship for causality and the event with the highest severity. A summary of TEAEs leading to discontinuation will also be provided.

A by-subject listing of any SAEs will be provided and all SAEs will be summarized by severity and relationship to study treatment.

Clinical laboratory test results will be summarized by visit and if applicable a shift table will be used to evaluate the shift in status from baseline at each visit.

9.5. Interim Analyses

A formal interim analysis of the data will be performed 8 weeks after the last LCL treatment.

9.5.1. Data Review Committee (DRC)

Cohorts 1 and 2 will be enrolled simultaneously. Safety data and subject photographs will be evaluated by the DRC at 4 weeks after LCL treatment in Cohorts 1 and 2 before a decision is made to move forward with the next and subsequent doses. The DRC will reconvene again after the last subject in Cohort 3 reaches the Week 4 Visit. Safety data will be monitored throughout the study by the DRC at regular intervals.

Dose escalation for LCL may be stopped at the discretion of the DRC as outlined in the DRC Charter.

The full details for the roles and responsibilities of the DRC will be detailed in the study-specific DRC charter.

10. Records Management

10.1. Data Collection

For this study, all protocol-specified data will be recorded in the source documents, and data will be entered on the eCRFs from the source documents. In addition to signature confirmation that a subject meets the study eligibility criteria, upon each subject's completion of the study, the investigator will sign a statement indicating that all pages of the subject's case report have been reviewed. Signature stamps and "per signatures" are not acceptable.

It is Revance's policy that the study data be verifiable with the source data which necessitates access to all original recordings, laboratory reports, and other records for each subject. The investigator must, therefore, agree to allow access to subjects' records, and source data must be made available for all study data. Subjects (or their legal representatives) must also allow access to their medical records. Subjects will be informed of the importance of increased record access and permission granted by signature on the informed consent document prior to any screening procedures.

Checks will be performed to ensure the quality, consistency, and completeness of the data. Instances of missing or un-interpretable data will be resolved with the investigator or study coordinator. Data queries will be sent to the study center. Site personnel will be responsible for providing resolutions to the data queries and for correcting the eCRFs, as appropriate. All unused Revance or designee study materials and binders must be returned to Revance or designee upon completion of the study.

The investigator must keep written or electronic source documents for every subject participating in the clinical study. The subject file that identifies the study in which the subject is participating must include the subject's available demographic and medical information including:

- Name
- Contact information
- Date of birth
- Sex
- Medical history
- Concomitant diseases
- Concomitant therapies/medication
- Study visit dates
- Performed examinations, evaluations, and clinical findings
- Investigational product administration
- AEs, SAEs, or pregnancy (as applicable)

Additionally, any other documents with source data, especially original printouts of data that were generated by technical equipment must be included in the subject's source document (e.g., laboratory value listings). All these documents must have at least the subject's initials, study number, and the date of the evaluation.

The data recorded during the study will be documented in the eCRF and/or the study-specific forms. Before or at study termination, all data must be forwarded to Revance or designee. The data will be recorded, evaluated, and stored in anonymous form in accordance with data-protection regulations.

Subjects will authorize the use of their protected health information (PHI) during the informed consent process in accordance with the applicable privacy requirements. Subjects who deny permission to use and disclose PHI will not be eligible to participate in the study. The investigator will ensure that the study documents forwarded to Revance or their designee, and any other documents, contain no subject names or other PHI, such as medical record number or date of birth.

Any amendments and corrections necessary will be undertaken in both the source documents and eCRFs (as appropriate) and countersigned by the investigator, or documented designee, stating the date of the amendment/correction. Errors must remain legible and may not be deleted with correction aids. The investigator must state his/her reason for the correction of any data. In the case of missing data/remarks, the entry spaces provided in the eCRF should be cancelled out to avoid unnecessary follow-up inquiries.

Regulatory authorities, the IRB/IEC and/or Revance's Quality Assurance department (or designee) may request access to all source documents, eCRFs, and other study documentation for on-site audit or inspection. The investigator must guarantee direct access to these documents. eCRFs will be kept by Revance or designee in a secured area. Clinical data will be recorded in a computer format for subsequent statistical analyses. Data files will be stored on electronic media with a final master data file kept by Revance or designee after descriptive and statistical analyses and reports have been generated and are complete.

10.2. File Management at the Study Center

It is the responsibility of the investigator to ensure that the study center maintains all source and essential documents in accordance with ICH Guidance for Industry E6 Good Clinical Practice: Consolidated Guidance, Section 8 – Essential Documents for the Conduct of a Clinical Study.

10.3. Records Retention at the Study Center

It is a Revance requirement that all investigators participating in clinical studies maintain detailed clinical data for one of the following periods:

- Country-specific requirements, or
- A period of at least 2 years following the last approval of a marketing application approved by a Regulatory Authority in an ICH region or until there are no pending or contemplated marketing applications in an ICH region, or,
- A period of 2 years after Revance notifies the investigator that the data will not be submitted for review by any Regulatory Authority

Regardless of applicable retention period, the investigator must not dispose of any records or essential documents relevant to this study without either (1) written permission from Revance, or (2) providing an opportunity for Revance to collect such records. The investigator shall take responsibility for maintaining adequate and accurate electronic or hard copy source documents of

all observations and data generated during this study. Such documentation is subject to inspection by Revance or designee and relevant regulatory agencies. If the investigator withdraws from the study (e.g., relocation, retirement) all study-related records should be transferred to a mutually agreed upon designee. Notice of such transfer will be provided to Revance in writing.

12. ETHICS AND RESPONSIBILITY

This study must be conducted in compliance with the protocol, the ICH Guidance for Industry E6 (R2) Good Clinical Practice: Consolidated Guidance and the applicable regulatory requirements. investigators must submit all essential regulatory documentation, as required by local and national regulations (including IRB/IEC approval of the protocol and ICF) to Revance or designee before investigational product will be shipped to the study center.

[REDACTED]

1. INTRODUCTION

The efficacy and safety of onabotulinumtoxinA for the treatment of lateral canthal lines (LCL) has been evaluated in a large-scale clinical development program consisting of 3 phase 3 studies (Carruthers, 2015b). Study 1 evaluated onabotulinumtoxinA for the treatment of LCL alone in a total of 445 subjects. Study 2 was a 7-month, double-blind, randomized, placebo-controlled, parallel-group study with 2 treatment cycles of onabotulinumtoxinA or placebo in a total of 917 subjects. Study 3 was a 5-month, double-blind, randomized, parallel-group, placebo-controlled extension study of the subjects who completed Study 2.

The Sponsor, Revance Therapeutics, Inc. (Revance), has conducted 5 studies to examine the safety and

This study will complement the available data from the dose-ranging GL and forehead lines study to provide a better understanding of the safety and efficacy of DAXI for injection in the treatment of the upper face rhytides.

This statistical analysis plan (SAP) describes the objectives of the study and the safety and efficacy assessments that are collected. The safety endpoints and the efficacy endpoints are defined, and the statistical methods used to analyze them are presented. Table shells for the planned end-of-text tables, figures, and listings are included in a separate document, but the titles are specified following the text of the SAP.

2. STUDY OBJECTIVES

2.1 Objectives

[figure not shown]
2.1.1 Primary Objective

The primary study objective is to evaluate the efficacy and safety of DAXI for injection in the treatment of dynamic lateral canthal lines (LCL).

2.2 Trial Endpoints

2.2.1 Efficacy Endpoints

The primary efficacy endpoint is the proportion of subjects achieving a score of 0 or 1 (none or mild) in LCL severity at maximum smile at Week 4 after LCL treatment on the Investigator Global Assessment of Lateral Canthal Wrinkle Severity (IGA-LCWS) scale.

2.2.2 Safety Endpoints

The primary safety endpoint is the incidence, severity, and relationship to study drug of TEAEs and SAEs during the overall study duration.

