This is a phase 2a, multicenter, open-label, dose-escalation study to evaluate the safety and efficacy of DAXI for injection for the treatment of subjects with moderate to severe LCL. This study will be conducted at 4 sites in the United States.

Approximately 64 subjects (18 to 65 years old) with moderate to severe LCL will be enrolled sequentially into 1 of 4 treatment cohorts (approximately 16 subjects per cohort) [REDACTED]

[REDACTED] Investigators will make all reasonable efforts to enroll equal proportions of subjects with moderate and severe LCL (based on baseline assessments) in each dosing cohort.

The total study duration will be up to 38 weeks, including up to 2 weeks for screening. Subjects will be followed for a minimum of 24 weeks from LCL treatment and up to 36 weeks or until scores on the maximal expression IGA-LCWS and PLCWS return to baseline, whichever occurs first. Subjects will then have a Final Evaluation Visit. Baseline, unless otherwise stated, refers to the last available assessment prior to LCL treatment (Day 1 Visit).

All treatments will be IM injections administered by the principal investigator (PI). [REDACTED]

[REDACTED]

[REDACTED]

[REDACTED]
 
[REDACTED]
 
[REDACTED]
 
[REDACTED]
 
[REDACTED] Revance has this right to stop or terminate the study at any time for any reason at their discretion or in consultation with the DRC.

Study Visits:
 
Study visits will occur at the Screening Visit (Day -14), Treatment Visit (Day 1), a safety follow-up phone call at Week 1, and follow-up visits at Weeks 2, 4, 8, 12, 16, 20, 24, 28, 32, and 36. Baseline for all efficacy assessments, unless otherwise noted, will be the last available assessment prior to LCL treatment (Day 1 Visit).

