8.2.5. Final Evaluation Visit (Week 36) or Early Discontinuation

The following procedures must be performed and recorded at the Final Evaluation Visit for each subject. Following treatment, subjects will be followed for at a minimum of 24 weeks from LCL treatment and up to 36 weeks for safety or until maximal expression scores on the IGA-LCWS and PLCWS return to baseline or Week 36, whichever occurs first. Subjects will then have a Final Evaluation Visit at which time the following procedures must be performed and recorded:

- [REDACTED]
- 2. Conduct patient education: Discuss the potential effect of DAXI for injection treatment, explain the PLCWS measurement and the categories of the severity assessment scales, and instruct the subjects to consider depth of lines for severity of their LCL. Use the provided Patient Education Brochure
- [REDACTED]
- 10. Perform a physical examination [REDACTED]
- [REDACTED]
- 12. Measure and record vital signs (body temperature, respiratory rate, sitting radial pulse, and sitting systolic and diastolic blood pressure)
- [REDACTED]
- 14. Collect blood and urine samples for clinical safety laboratory tests (hematology, serum chemistry, and urinalysis)
- [REDACTED]

If there are no safety concerns, the subject's participation in the study is complete at this visit.

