8.5.2. Assessment and Reporting Requirements

The investigator will assess each subject post-treatment and at each subsequent study visit for the occurrence of AEs. In order to avoid bias in eliciting AEs, subjects should be asked the following non-leading question: “How have you felt since your last visit?” All AEs (serious and non-serious) will be collected from the signing of the ICF until the Final Evaluation Visit. Any AE reported by the subject must be recorded on the source documents and eCRFs.

All AEs will be collected from Day 1 until Week 36 or the Final Evaluation Visit at all timepoints as specified in the SOA (Section 1.3). Medical occurrences that begin before the start of study intervention but after obtaining informed consent will be recorded as well.

All SAEs will be recorded and reported to Revance or designee immediately within 24 hours of their awareness of the event. All fatal or life-threatening SAEs should be telephoned to Revance or the designee’s authorized representative as soon as the investigator learns of the event.

[figure not shown]

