3. OVERALL STUDY DESIGN AND PLAN

3.1 Study Design

This is a phase 2a, multicenter, open-label, dose-escalation study to evaluate the safety and efficacy of DAXI for injection for the treatment of subjects with moderate to severe LCL. This study will be conducted at 4 sites in the United States.

[figure not shown]
[REDACTED]

[figure not shown]
Approximately 64 subjects (18-65 years of age) with moderate to severe LCL will be enrolled [REDACTED]

[figure not shown]
[REDACTED] The total study duration will be up to 38 weeks including up to 2 weeks for screening. Subjects will be followed for a minimum of 24 weeks and up to 36 weeks or until scores on the IGA-LCWS and PLCWS return to baseline (Day 1 Visit) or until Week 36, whichever occurs first. Subjects will then have a Final Evaluation Visit. [REDACTED]

[REDACTED]

A Data Review Committee (DRC) will be used to review available data and will determine whether to proceed to the subsequent cohorts. Cohorts 1 and 2 will be enrolled simultaneously and the DRC will review data 4 weeks after LCL treatment for the last subject in Cohorts 1 and 2. The DRC will convene again after the last subject in Cohort 3 reaches the Week 4 visit.

Statistical Analysis Plan for 1820205

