6.6 Safety Analyses

Safety summaries and analyses will be performed on the Safety population and will be presented by cohort and in total across cohorts. Descriptive statistics will be presented to summarize the safety data. By visit safety summaries will use denominators based on the number of subjects with valid observations at that visit unless otherwise specified.

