6.6.3 Adverse Events

All AEs will be recorded and classified on the basis of MedDRA terminology. All treatment-emergent AEs will be summarized by summary cohort and overall, system organ class, preferred term, severity, and seriousness. When summarizing events by causality and severity by subject, each subject will be counted only once within a system organ class or a preferred term by using the event with the greatest relationship and highest severity within each classification. In the case of missing AE severity or relationship, the most severe/highest relationship will be imputed. Additionally, some summaries will present the number of AEs as well as incidence.

An overall summary of treatment-emergent AEs (TEAEs) will be provided. The number and percentage of subjects experiencing an AE, an SAE, a related AE, a related SAE, an AE of special interest, an AE leading to study discontinuation, and an AE resulting in death will be summarized.

All information pertaining to AEs noted during the trial will be listed by subject, detailing the verbatim description given by the Investigator, preferred term, system organ class, start date, stop date, severity, action taken regarding trial drug, corrective treatment, outcome, and drug relatedness. The event onset relative (in number of days) to the date of treatment for LCL, as well as to the date of last treatment administration prior to the event, will be provided. In addition, a list of adverse events that lead to the subject's premature discontinuation of the trial will be provided. Serious adverse events (SAEs) will be listed by subject.

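### Crude TEAE incidence over the whole study is compared across doses although follow-up after Week 24 depends on duration of effect; a common Day 1 to Week 24 window removes the artefact

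*SAP*

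**What the plan says.** The primary safety endpoint (SAP 2.2.2) is: "The primary safety endpoint is the incidence, severity, and relationship to study drug of TEAEs and SAEs during the overall study duration".

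The overall study duration is not the same for every subject. The synopsis of the Protocol (Overall Design) gives the range: "Subjects will be followed for a minimum of 24 weeks from LCL treatment and up to 36 weeks". Protocol 8.2.5 adds the exit rule: "until maximal expression scores on the IGA-LCWS and PLCWS return to baseline or Week 36, whichever occurs first". SAP 3.1 has the same range and the same rule for ending follow-up: "return to baseline (Day 1 Visit) or until Week 36, whichever occurs first".

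Adverse-event collection follows that subject-specific end. Protocol 8.5.2 states: "All AEs will be collected from Day 1 until Week 36 or the Final Evaluation Visit at all timepoints".

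For the analysis, SAP 6.6 states: "Safety summaries and analyses will be performed on the Safety population and will be presented by cohort and in total across cohorts". The overall summary in SAP 6.6.3 is "The number and percentage of subjects experiencing an AE, an SAE, a related AE, a related SAE" and further categories of the same kind, with event counts in some tables. The readable text gives no common adverse-event window, person-time rate or time-to-first-event analysis. SAP 6.6 adapts denominators to the subjects observed only for by-visit summaries.

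Two related items are planned. SAP 6.1 summarises duration of participation, and SAP 6.6.3 lists each event's onset day relative to treatment. Neither is tied to the incidence tables.

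**The concern.** The exit rule is essentially the event in the duration endpoint of SAP 6.5.3.2, return to baseline on both scales at maximum smile. Subjects whose effect lasts longer stay in the study longer and have more time in which to report a first adverse event. If duration depends on dose, so does time at risk after Week 24.

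The plan intends doses to be compared on safety. Protocol 9.1 says the data can be used to assess the maximal tolerable dose level, and the synopsis commits to adverse-event summaries by dose group. Unequal follow-up could create or exaggerate a dose gradient in crude percentages, or make a real one harder to read.

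**Working it through.** **No planned figure to reproduce.** The documents state no expected TEAE rate, and the sample size is not based on power (SAP 3.1.1). The readable figures agree with each other: 2 + 36 = 38 weeks and 4 × 16 = 64 subjects.

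**Inputs from the documents**
- Minimum follow-up 24 weeks, maximum 36; clinic visits from the minimum onward at Weeks 24, 28, 32 and 36 (Protocol 4.4).
- About 16 subjects per cohort (Protocol 4.1).
- Adverse-event incidence in the comparator programme described in Protocol 2: 58.2% over one year, and 58.1% for its first two studies.

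**Assumptions, not figures for this trial**
- The comparator rates apply here.
- The 58.1% refers to 7 months, or 7 × (365.25/12)/7 = 30.4 weeks.
- The hazard is the same at every dose, so any difference below is artefact.

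**Step 1: constant hazard, extreme contrast.** With λ = −ln(1 − p)/T, incidence by week t is 1 − exp(−λt).

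| Calibration | λ per week | Week 24 | Week 28 | Week 32 | Week 36 | 36 minus 24 |
|---|---|---|---|---|---|---|
| 58.2% in 52 weeks | 0.01677 | 33.1% | 37.5% | 41.5% | 45.3% | 12.2 points |
| 58.1% in 30.4 weeks | 0.02861 | 49.7% | 55.1% | 60.0% | 64.3% | 14.6 points |

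This is everyone leaving at Week 24 against everyone staying to Week 36. It amounts to 16 × 0.122 = 1.95, or 16 × 0.146 = 2.3, extra affected subjects per cohort.

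**Step 2: a less extreme contrast.** Let time to return to baseline be Weibull with shape 3 and median m (assumed), so S(t) = exp[−ln 2 × (t/m)³], with exit at the first visit from Week 24 on.
- m = 20: exits at Weeks 24/28/32/36 are 69.8/15.3/9.1/5.8%, mean follow-up is 26.0 weeks, and incidence at the lower λ is 35.3%.
- m = 28: exits are 35.4/14.6/14.5/35.5%, mean follow-up is 30.0 weeks, and incidence is 39.3%.
- Difference: 4.0 points, or 0.6 of a subject in 16.

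**Step 3: events clustering early.** Keep one-year incidence at 58.2%, so H = −ln(0.418) = 0.872. Place a fraction f of H in the first 4 weeks and spread the rest evenly to Week 52. Cumulative hazard is fH + (1 − f)H(t − 4)/48. The extreme contrast shrinks as follows:
- f = 0.50: 46.1% versus 51.7%, 5.6 points.
- f = 0.75: 52.5% versus 55.0%, 2.5 points.
- f = 0.90: 56.0% versus 57.0%, 0.9 points (rounded before subtraction, these read as 1.0).

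**Step 4: against sampling error.** In the extreme case the standard error of a difference is √(0.331 × 0.669/16 + 0.453 × 0.547/16) = 0.171, about 17 points. In 400,000 simulated pairs of cohorts with equal hazards, the longer-followed cohort had more affected subjects 70% of the time in the extreme case and 52% for medians of 20 versus 28 weeks. With equal follow-up the figure was 43%; the remainder is ties and reversals.

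**Step 5: candidate corrections.**
- *Common window to Week 24:* equal hazards give equal expected incidence, 33.1% and 33.1%, so the artefact is zero whatever the hazard shape.
- *Subject-time rate:* it equalises the doses only if the hazard is constant (1.68 first events per 100 subject-weeks in both). Suppose instead an assumed 50% incidence at Week 36 with half the cumulative hazard in the first 4 weeks. Incidence at Week 24 is then 1 − exp[−ln 2 × (0.5 + 0.5 × 20/32)] = 43.1%. The crude ratio is 0.50/0.431 = 1.16, but the rate ratio is (0.50/36)/(0.431/24) = 0.77. The bias is reversed. Stopping subject-time at the first event still gives about 0.83.

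**The case against.** The strongest case on the other side has five parts.

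1. *Only the tail differs.* All completers share the first 24 weeks. Injection-site reactions are checked on the same early schedule for everyone (Day 1, Weeks 2 and 4). Protocol 2 describes the class effect as usually lasting 4 to 5 months, shorter than the 24-week minimum, so follow-up could turn out nearly equal. This stands, and it bounds the artefact. It does not remove it: the endpoint covers all TEAEs, most comparator events were judged unrelated to treatment, and such background events can plausibly accrue with time.
2. *The artefact is smaller than the noise.* With 16 per cohort and no formal tests planned (Protocol 9.4), even 12 points is below one standard error. This stands. But the artefact is systematic, and readers of a descriptive table compare raw percentages.
3. *Late events may be real.* Protocol 8.2.5 describes follow-up to 36 weeks as being for safety, and events arising while a longer effect persists are a consequence of that dose. This stands, and is why those events must stay visible in their own table.
4. *The cut can be made later.* Onset days are listed. True, but specifying the window in advance avoids choosing it after the data are seen.
5. *Redaction.* SAP Section 9, the table list, cannot be read, and parts of Sections 5 and 6 are blacked out. A windowed table may already exist.

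A reader might also infer that dose escalation is distorted. The documents do not support that. The Data Review Committee's decisions are timed to Week 4 (Protocol 4.1 and 9.5.1; SAP 3.4.1), and the return-to-baseline rule cannot release anyone before Week 24.

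**Conclusion.** The point holds as a limited one. The readable plan compares crude incidence by cohort over a follow-up that, after Week 24, depends on duration of effect. If duration differs by dose, the longer-acting dose is expected to show the higher percentage even with equal hazards.

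It would go too far to say that a longer-acting dose will show more adverse events merely from being watched longer. That requires first events to begin after Week 24 and doses to differ in the share of subjects still above their exit criterion then; the readable documents establish neither. The 12 to 15 points are a ceiling under the assumed comparator rates, a flat hazard and the all-24 versus all-36-week contrast. The 4-point figure rests on assumed medians and an assumed Weibull shape, and early clustering reduces even the extreme contrast to between 0.9 and 5.6 points.

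The effect is confined to the final descriptive dose comparison. A change is still worth making because the direction is predictable and the remedy is cheap, subject to the caveat about the unreadable table list.

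**What to change.** In SAP 2.2.2 and 6.6.3:
- Specify that TEAE and SAE incidence is compared across doses on the common window Day 1 to Week 24. State the cut as a study day or as the Week 24 visit, since Protocol 8.2.6 allows that visit to vary by 4 days either way.
- Show events with onset after Week 24 in a separate table by dose, with the number of subjects still in follow-up as the denominator.
- Keep whole-study incidence as a reported table, with a note that follow-up differs by subject.
- Do not rely on a subject-year rate as the correction, because it over-corrects when events come early.

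The cost is one onset-window flag and the additional table output. No visit, assessment or data item changes. The drawback is that late events sit outside the main cross-dose comparison. The window also does not address subjects who withdraw before Week 24, so their number should be shown by dose beside the table. If Section 9 already lists a windowed table, the change reduces to naming it in 2.2.2 and 6.6.3 as the basis for comparing doses.
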